# List of abbreviations and relevant definitions

---

Abbreviation	Definition
ABR	ABR form, General Assessment and Registration form, is the application form that is required for submission to the accredited Ethics Committee (In Dutch, ABR = Algemene Beoordeling en Registratie)
AE	Adverse Event
AF	Atrial Fibrillation
AR	Adverse Reaction
CA	Competent Authority
CCMO	Central Committee on Research Involving Human Subjects; in Dutch: Centrale Commissie Mensgebonden Onderzoek
CV	Curriculum Vitae
DSMB	Data Safety Monitoring Board
EU	European Union
EudraCT	European drug regulatory affairs Clinical Trials
GCP	Good Clinical Practice
IB	Investigator's Brochure
IC	Informed Consent
IMP	Investigational Medicinal Product
IMPD	Investigational Medicinal Product Dossier
INR	International Normalised Ratio
METC	Medical research ethics committee (MREC); in Dutch: medisch ethische toetsing commissie (METC)
NOAC	Non-VKA (or Novel) Oral Anticoagulant
RCT	Randomised Controlled Trial
(S)AE	(Serious) Adverse Event
SPC	Summary of Product Characteristics (in Dutch: officiële productinformatie IB1-tekst)
Sponsor	The sponsor is the party that commissions the organisation or performance of the research, for example a pharmaceutical company, academic hospital, scientific organisation or investigator. A party that provides funding for a study but does not commission it is not regarded as the sponsor, but referred to as a subsidising party.
SUSAR	Suspected Unexpected Serious Adverse Reaction
TTR	Time with INR in therapeutic range
VKA	Vitamin K antagonists
VTE	Venous thrombo-embolism
Wbp	Personal Data Protection Act (in Dutch: Wet Bescherming Persoonsgegevens)
WMO	Medical Research Involving Human Subjects Act (in Dutch: Wet Medisch-wetenschappelijk Onderzoek met Mensen)

---

# Summary

---

## Rationale

40% of patients using anticoagulants is eighty years or older. In this vulnerable age group there is a delicate balance between haemorrhages and thrombosis. Good quality of anticoagulation is of paramount importance, but this is less frequently achieved with higher age. Decreasing acenocoumarol dosage may cause a higher variability. We hypothesise that dosing using tablets of half a milligram acenocoumarol increases anticoagulation control.

## Objective

The main objective is to collect data on effect size for, and determine the feasibility of, a full scale RCT to assess the effect of dosing per 0.5 mg acenocoumarol on quality of anticoagulation, treatment satisfaction, and medication errors.

## Study design

Randomised controlled trial, with 2 treatment groups (see below) with 40 patients each.

## Study population

Patients aged 80 and above, who have been managed by Certe Trombosedienst for over 9 months, and use a daily dose of acenocoumarol between 0.5 and 2.0 milligram for any indication.

## Intervention

One group is dosed using tablets of 0.5 milligrams of acenocoumarol, while the other group uses the regular 1.0 milligram tablets. Both will be dose-adjusted to their previously determined INR target range.

## Main study parameters/endpoints

The main study parameter is quality of anticoagulation (individual time in therapeutic range and INR variability).

## Nature and extent of the burden and risks associated with participation, benefit and group relatedness

Patients already use dose-adjusted acenocoumarol, so we do not expect an added risk caused by the drug. All patients will be visited and administered a short questionnaire twice for the study. The intervention group will on average have to take twice as many tablets of acenocoumarol as before. This research will yield data relevant for the participating patients and other, similar patients.

# 1. Introduction and rationale

---

40% of patients using anticoagulation (VKA) is eighty years or older. Their share will further increase because the population ages, and indications for anticoagulation are more often acknowledged. However, the elderly are a vulnerable group. The risks of both haemorrhages and thrombosis increase with age (70% increase of those aged 75 and older, compared with those under 75 [1]). The HARM investigation[2] showed VKA are one of the most dangerous medication groups for medication-related hospitalisation.

Good anticoagulation control optimises the benefits and minimises the risks. Parameters such as time spend in therapeutic range (iTTR) and variability are a strong intermediary for clinical outcomes [3,4]. Good quality of anticoagulation is therefore of paramount importance.

Unfortunately, our own research shows that quality of anticoagulation decreases with age[5]. This is also true amongst the elderly: patients aged 80 and above are worse controlled than those aged 70-79. A possible cause is the diminishing acenocoumarol dose required with higher age. In our study it declined from on average 2.3mg in patients aged 70-79, to 1.9mg for those aged 80-89, to 1.6mg for those aged 90 or older[5]. This has to do with nutritional state, body composition and comorbidity. Because acenocoumarol is only available in tablets of 1 milligram, it is harder to spread out low doses over the week evenly. The scheme 1-2-1-2 causes larger relative differences than 2-3-2-3. Indeed, in our data we saw a lower iTTR but above all a higher variability in patients using less than 2 milligrams of acenocoumarol per day, versus those with a higher dosage.

In other words, usual care for elderly does not achieve the same quality as for younger patients, despite higher commitment of the thrombosis service, more frequent INR controls and more home visits. These interventions cost money, and -more importantly- lower quality of anticoagulation causes more thrombotic complications and haemorrhages[3,4]. Patients in the lower quarter of anticoagulation control are three times as prone to thrombotic complications or haemorrhages as the other 75%[3].

We hypothesise that more precise dosing regulation using tablets of 0.5 milligrams of acenocoumarol will increase quality of anticoagulation. If smaller dosing units for acenocoumarol lead to better anticoagulation control, the available care for patients using acenocoumarol can be directed more appropriately: fewer interventions might be needed in the growing group of patients aged 80 and above.

## 2. Objectives

---

The **primary objective** is to collect data on effect size for, and determine the feasibility of, a full scale RCT with the aims:

1. To evaluate the effect of smaller dosing units on quality of anticoagulation;
2. To evaluate if this alters treatment satisfaction
3. To evaluate if this prevents or causes errors in medication intake.

## 3. Study design

---

We propose an open-label, prospective, randomised controlled trial.

Many patients visit, or are visited by, the Thrombosis Service regularly for INR measurements. A day later they will receive a new dosing calendar via regular mail, with an overview of the daily dosages in the period until the next INR measurement. Potentially eligible patients selected by the Thrombosis Service (based on age and acenocoumarol dose) will be handed out an information letter about our study and a response card during one of these regular visits. Patients who express their interest in participating in the study will be visited by research personnel to inform them about the study, answer all questions, and collect informed consent. After consent, the subject will be randomised into one of two groups:

- **Intervention group:** dosing using tablets of 0.5 mg acenocoumarol
- **Control group:** dosing using the regular tablets of 1.0 mg acenocoumarol

Allocated treatment will begin the same day, and will last until the end of study visit six months later. The system of “therapy control” with INR-based dosage adjustments will not differ from everyday care in both treatment groups, only the dosing steps might differ. Directly following randomisation, and during the end-of-study-visit, subjects will fill in the PACT-Q2 questionnaire[6], a questionnaire developed specifically to assess patients’ perception of anticoagulation treatment.

We opt for a RCT (instead of for instance a before and after comparison) to avoid the “Hawthorne effect” (the phenomenon that quality would improve simply because one participates in a study). Due to the nature of the medication and its monitoring, it would be very difficult to do this in a blinded fashion. Because we use an objective endpoint, we do not foresee bias there. For the subjective measurements of patient satisfaction, unblinded assessment is crucial as the larger number of tablets is inherent to the intervention.

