### 8.2 Randomisation, blinding and treatment allocation

The study personnel will perform randomisation on-the-spot. To avoid technical difficulties, we will perform randomisation using ordered envelopes. We will stratify by INR target range (2.0-3.0 versus 2.5-3.5) within pre-specified blocks. The University Medical Center Groningen Pharmacy will provide randomisation lists.

Patients and professionals at the thrombosis service will know to which treatment group the patient has been randomised.

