## 10. Statistical analysis

---

The data will be analysed in accordance with a statistical analysis plan that will be made before database lock. Due to the nature of this study, no formal statistical testing will be performed.

We will describe the primary endpoint parameters (iTTR, variance growth rate, SDTinr) by treatment group. The secondary endpoint parameter treatment satisfaction will be calculated as the difference between the score at randomisation and that at the end of study visit. This difference will be described per treatment group. The parameter medication errors will be summarised per treatment group and error severity.

To determine the feasibility of a full-scale RCT, we will calculate the size of the required patient population, based on the following assumptions and parameters:

- Significance level 0.05
- Power 0.80
- Effect size equal to the one found in this trial
- Inclusion ratio equal to the one found in this trial (i.e. percentage of selected patients that enrolls in the trials)

We will not perform interim analyses.

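### The first PACT-Q2 is completed after patients learn their open-label allocation, so the baseline of the satisfaction change score is open to a shift that differs by arm

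*Protocol*

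**What the plan says.** Section 3 of the protocol sets the design ("We propose an open-label, prospective, randomised controlled trial") and the timing of the satisfaction questionnaire: "Directly following randomisation, and during the end-of-study-visit, subjects will fill in the PACT-Q2 questionnaire". On treatment start it adds: "Allocated treatment will begin the same day".

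Section 8.2 describes how allocation is made, using ordered envelopes: "The study personnel will perform randomisation on-the-spot". On who is aware of the result it says: "Patients and professionals at the thrombosis service will know to which treatment group the patient has been randomised".

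The schedule in Section 8.3 puts consent, the check of criteria, randomisation, PACT-Q2 and start of treatment in one study-visit column, with the rows in that order.

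Section 10 defines the satisfaction endpoint, which "will be calculated as the difference between the score at randomisation and that at the end of study visit". It continues: "This difference will be described per treatment group". The same section rules out formal testing. Section 8.1.2 lists treatment satisfaction as a secondary parameter.

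**The concern.** A change score compares arms fairly only if its starting value could not have been influenced by the allocation. Here the patient has just learned whether to stay on the usual 1 mg tablets or move to 0.5 mg tablets, which the Summary says means about twice as many tablets on average. PACT-Q2 asks how patients perceive their anticoagulation treatment, so pleasure, disappointment or reluctance at that news could enter the first answers, and could do so unequally in the two arms. The difference in change would then combine the effect of the tablets with the reaction to being allocated them.

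The protocol fixes both the order of collection and the change score. A later analysis plan cannot supply a pre-allocation score that was never collected. The pilot is also meant to prepare a full-scale trial whose second aim concerns treatment satisfaction (Section 2), and the same visit order could be carried into it.

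**Working it through.** **Order of events.** The protocol states no PACT-Q2 figure, so the first step is to set the sections side by side.

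| Step | Source | Content |
|---|---|---|
| Allocation | Section 8.2 | At the visit, from ordered envelopes; patient knows the result |
| First PACT-Q2 | Section 3 | Directly after randomisation |
| Start of treatment | Sections 3 and 8.3 | Same day; listed below PACT-Q2 in the schedule |
| Second PACT-Q2 | Sections 3 and 8.3 | End-of-study visit at six months |
| Endpoint | Section 10 | Difference between the two scores, by arm |

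No section provides a PACT-Q2 before randomisation. The first score is exposed to knowledge of the allocation. On the schedule's row order it is not exposed to experience of the allocated tablets.

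**Effect on the change score.** Take change as end of study minus first score. Let D be the true between-arm difference at month 6 (intervention minus control), and b the between-arm difference in first score caused by knowing the allocation. Randomisation makes the expected difference zero otherwise. Then:

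- expected difference in change = D − b.

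The documents give no PACT-Q2 mean or SD, so the values below are assumptions chosen to show the range:

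| b (points) | D = 0 | D = 5 |
|---|---|---|
| −5 | +5 | 10 |
| −2 | +2 | 7 |
| 0 | 0 | 5 |
| +2 | −2 | 3 |
| +5 | −5 | 0 |

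With D = 5, a shift of +5 hides the effect and a shift of −5 doubles it.

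**Would adjustment repair it?** With equal SDs and correlation ρ between the two scores, the baseline-adjusted difference has expectation D − ρb. For D = 5 and b = +5 this gives:

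- ρ = 0.3: 5 − 1.5 = 3.5
- ρ = 0.5: 5 − 2.5 = 2.5
- ρ = 0.7: 5 − 3.5 = 1.5

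The unadjusted change score gives 0 and the truth is 5, so part of the bias remains in every case.

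**Check by simulation** (200,000 patients, assumed ρ = 0.5, D = 0, b = −0.3 SD):

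| Analysis | Expected | Simulated |
|---|---|---|
| Change score | +0.30 SD | +0.305 SD |
| Baseline-adjusted | +0.15 SD | +0.154 SD |
| Month-6 score only | 0 | +0.004 SD |

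The month-6 comparison does not use the first score, so the timing does not bias it.

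**Can b be seen in the data?** The between-arm difference in first scores estimates b plus chance imbalance. With 40 patients per arm its standard error is √(2/40) = 0.22 SD, so a 95% interval extends about 1.96 × 0.22 = 0.44 SD either side. A shift of 0.3 SD could not be told from chance.

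**The case against.** The strongest reply is that little depends on this score. It is a secondary parameter, described by arm without testing, and Section 10 specifies no between-arm contrast of change scores; the reader would form that contrast. Everyone enrolled has used acenocoumarol for more than nine months (Section 4.3) and answers before trying the new tablets, so a large shift is not a given. Section 3 also argues that unblinded assessment of satisfaction is needed because the tablet count is part of the intervention.

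Most of this stands as a limit on importance, but it does not defend the order. The argument in Section 3 justifies an unblinded month-6 score; it gives no reason to reveal the allocation before the first one. Results set out by arm in a randomised trial will be compared.

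It is also fair to say that the schedule is weak evidence of sequence: its items share one column, and the INR measurement and dose adjustment come last in the list. It is consistent with Section 3, but only Section 3 states the order outright.

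Four stronger conclusions are tempting, and the documents support none of them:

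- **That the baseline is shown to be distorted.** It is open to a differential shift; nothing establishes that one occurs, or in which direction.
- **That the damage is beyond repair.** Both randomised arms complete the month-6 questionnaire, and those scores can be compared without this bias.
- **That adjustment is useless.** It reduces the bias, to an extent that depends on the correlation.
- **That satisfaction is an objective of this pilot in its own right.** The numbered aims in Section 2 belong to the future full-scale trial; the pilot's objective is to collect effect-size data and judge feasibility.

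**Conclusion.** The point holds as a modest design flaw that costs nothing to correct. The sequence is certain from Sections 3 and 8.2, and Section 10 builds the satisfaction endpoint on a score taken after the allocation is known. Any differential shift b passes one for one, with opposite sign, into the between-arm difference in change. This assumes an additive shift in the first score, and change taken as end minus start; with the reverse subtraction, the signs of the contrast and the bias both flip. The size of b cannot be derived from the documents, and the point values above are illustrations only.

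The consequence is confined to how a descriptive secondary endpoint is read, and to what the pilot passes on to the second aim of the full-scale trial. iTTR and INR variability do not depend on the questionnaire, and the sample size in Section 4.4 rests on TTR alone.

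**What to change.** 1. In Section 3 and the Section 8.3 schedule, place the first PACT-Q2 after informed consent and the eligibility check, and before the envelope is opened.
2. In Section 10, define the starting value of the change score as the score taken before randomisation.
3. For any patient whose first PACT-Q2 was already completed after allocation, also describe the month-6 scores by arm without the first score.

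The first two changes keep the same visit and the same questionnaire, with no added burden for patients; only the order and the wording change. The third adds one descriptive summary by arm from data already planned. Its precision relative to the change score depends on the correlation: the variance of a change is 2(1 − ρ) times that of a single score (equal SDs), so the two are equally precise at ρ = 0.5 and the month-6 score is less precise only above that.

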## 4. Study population

---

### 4.1 Population (base)

Certe Trombosedienst is the largest thrombosis service in Groningen. It treats 8000 patients aged 80 or older, of whom 55% (4400 patients) uses less than 2 milligrams of acenocoumarol per day.

### 4.2 Inclusion criteria

In order to be eligible to participate in this study, a subject must meet all of the following criteria:

- Using acenocoumarol for any indication, and being managed by Certe Trombosedienst
- 80 years of age or older at time of inclusion
- Using acenocoumarol with an average daily dose of less than 2 milligrams in the previous three months
- Subject provided informed consent

### 4.3 Exclusion criteria

A potential subject who meets any of the following criteria will be excluded from participation in this study:

- Initiated therapy with acenocoumarol in the last nine months
- Expected termination of VKA within six months
- Dosing step lower than or equal to "step 7", i.e. usage of less than 3.5 milligrams acenocoumarol per week. Patients who use such a low dose generally have an unfavourable prognosis.
- Patients who determine the acenocoumarol dose themselves

## 4.4 Sample size calculation

We performed a power analysis for a larger follow-up study, based on the following parameters:

Parameter	Value	Standard deviation
TTR control group	69 %	19
TTR intervention group	72.5%	17
Alpha (type I error rate)	5 %	
Failure rate	10 %	
Power (1 - type II error rate)	80 %	

The TTR values above are based on observational findings in our clinical practice. It should however be noted that the INR target ranges have been modified (c.q. narrowed) as per January 1st, 2016, and that we expect this will affect the TTR in both groups. This underlines the necessity of a pilot study.

This resulted in a needed sample size of 917 patients, which is much less than the 140 000 patients aged 80 and above managed by the Dutch Thrombosis Services.

For this pilot study we want to randomise 2 x 40 patients. This should give us an overview of the point estimates in the power analysis (which are currently based on observational data), and -more importantly- about the time investment needed to conduct a larger-scale study. Due to the inter-individual variation in response to VKA, we think a smaller sample could distort the view.

## 5. Treatment of subjects

---

### 5.1 Investigational product/treatment

Both treatment groups will be treated with acenocoumarol:

- the control group will be treated with regular, registered 1 mg tablets ([Summary of the Product Characteristics](#)).
- for the intervention group, tablets of 0.5 milligrams will be manufactured by the UMCG Pharmacy in accordance with ICH-GMP[7] and the regulations imposed by the WMO and the *Geneesmiddelenwet*.

### 5.2 Use of co-intervention

There are no co-interventions in this study.

## 6. Investigational product

---

### 6.1 Name and description of investigational product(s)

Acenocoumarol is a vitamin K antagonist (VKA). VKA have an anticoagulant effect by interfering with the cyclic interconversion of vitamin K, which leads to a vitamin K depletion which lowers the production of vitamin K-dependent proteins including coagulant factors II, VII, IX and X. This results in less formation of thrombin and fibrin. The half-life of acenocoumarol typically is 8 to 11 hours ([Farmacotherapeutisch Kompas](#)). The liver inactivates the active substances followed by renal and faecal excretion. VKA only interfere with the production of new coagulation factors, and have no influence on already circulating factors. Therefore, due to the relative long half-life of factor II, the antithrombotic effect needs at least five days to reach full potential. Interactions with VKA are not uncommon: co-medication and food may influence the absorption, effect and inactivation of VKA. To monitor therapy, the thrombosis services determine the so-called international normalised ratio (INR) and adjust the dosage accordingly.

### 6.2 Summary of findings from non-clinical studies

There is ample experience and clinical data on acenocoumarol, so we refer to the [Summary of the Product Characteristics](#) and the clinical studies below.

## 6.3 Summary of findings from clinical studies

Because the mechanism of action of all VKA is similar (only half-lives differ), warfarin studies are considered also applicable to acenocoumarol.

Acenocoumarol has been an established treatment or prophylaxis for multiple indications:

- Atrial fibrillation [8–10]
- Venous thrombo-embolism [10,11]
- Valvular heart disease [12]

INR target range may differ between and within the indications. Usually the INR target range for “venous indications” is 2.0–3.0, while that for “arterial indications” is 2.5–3.5 or even higher.

Alternatives for VKA have been registered in the last years (NOAC: e.g. rivaroxaban, apixaban, dabigatran). While new guidelines favour NOAC over VKA for AF[13] and VTE[14,15], active switching of patients without problems is not recommended. Decreased renal function is a contra-indication for use of a NOAC: these most fragile patients will use VKA.

## 6.4 Summary of known and potential risks and benefits

Benefits of anticoagulant treatment is a lower incidence of thrombosis, but this comes at the expense of (major) bleeds. It is known that the better the quality of anticoagulation, the lower the overall risk of adverse outcomes[3,4]. The risk of major bleeding with VKA varies between 1.40 and 3.40% per year[16], but this increases with lower iTTR and higher age.

Because the active substance is the same in both treatment groups (which is the same as the one used in clinical practice), we do not expect any alterations in the potential risks and benefits of the pharmacological compound per se. Our hypothesis, however, suggests a net benefit of the intervention.

